194 i. Patients transitioning from once daily insulin glargine to once daily IDeg with
195 a bridging dose of insulin glargine.
196 ii. Patients transitioning from twice daily insulin glargine to once daily IDeg
197 with a bridging dose of insulin glargine.

198 **2. Direct-Conversion Groups:**

199 i. Patients transitioning from once daily insulin glargine to once daily IDeg
200 without a bridging dose of insulin glargine (but with a bridging dose of
201 placebo solution to preserve blinding).
202 ii. Patients transitioning from twice daily insulin glargine to once daily IDeg
203 without a bridging dose of insulin glargine (but with a bridging dose of
204 placebo solution to preserve blinding).

205
206 All patients will be instructed to use their own prescription insulin medications till before
207 the 1st dose of IDeg. On the night they have to transition to IDeg, they will start using
208 study drugs for their basal insulin (see section 3.10.4). Starting with the 1st dose of IDeg,
209 their basal insulin will be from study drug only, till visit #3 (see section 3.10.6), at which
210 time, they will resume their original insulin prescriptions. They will remain on their own
211 prescription short-acting insulin throughout the study. On the night of the transition, all
212 patients will be instructed to take their 1st dose of IDeg and along with this, they will take
213 a second injection from a pre-filled syringe of a pre-specified dose of insulin glargine or
214 matched placebo (normal saline), that participants will collect from Investigational Drug
215 Services Pharmacy (IDS) on the same day. The dose will be calculated ahead of time by
216 study staff on visit 2 (see under section 3.10.2.1). Neither the patients, nor the research
217 staff will be aware of their randomization, which will be done by IDS. Patients will act as
218 their own controls, as we will collect glycemic data from 48 hours prior to the first dose
219 of IDeg, which will be compared to the data seen in the 48 hours after the first dose of
220 IDeg. During this observation period of the 48 hours before and after the first dose of
221 IDeg, no adjustments will be made to the calculated and recommended doses of insulin
222 glargine or IDeg. Patients will be followed for up to 1 week after the first dose of IDeg.
223

224 **3.3 Rationale for study Design**

225 Though IDeg is being increasingly used in clinical practice, there are no guidelines on

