3.7 Withdrawal Criteria

Patients have the right to withdraw from the study at any stage and for any reason.

Patients **may be** discontinued prematurely, by the investigator for any of the following reasons:

- Emergence of a severe condition(s) such that, in the judgement of the investigator, continuation in the trial would negatively impact the health of the patient.
- Lack of compliance with study medication or visits as judged by the Investigator.
- Patient lost to follow-up.
- Major protocol violation.
- Inter-current illness that, in the judgment of the investigator, should result in premature discontinuation.
- Use of prohibited medications (see the Inclusion/Exclusion criteria)
- Onset of glucocorticoid burst/pulse therapy during the study period.
- Knowledge of new risks necessitating new benefit/risk evaluation.
- Patient voices intention to become pregnant in the immediate future.

Patients **must** be discontinued for any of the following reasons:

- If Novo Nordisk determines that the study must be stopped, all patients will be required to end participation at that time.
- Trial closed-out.
- Patient becomes pregnant.

A patient will not be discontinued early from the study solely because of missing the scheduled transition from insulin glargine to IDeg. The research staff will discuss the matter with the patient and determine whether they feel he/she can continue moving forward in the study following all study procedures, including dosing. If after this discussion, the patient and the research team are in agreement about continuing in the study, the investigator will decide if he/she may remain in the study.

A subject cannot be considered lost to follow-up until the research center performs and documents at least three (3) attempts to contact him by phone, email or letter.

323 **3.8 Patient Replacement**

324 Patients discontinuing from the study will not be replaced. IDS will continue to assign
325 randomization of the next participant to a specific group, based on the original
326 randomization plan, when the next participant has completed screening procedures and is
327 ready for randomization. We will include data from all randomized participants in our
328 data analysis.

329

330 **3.9 Rationale for Study Population**

331 The main objective of our study is to determine if the use of a bridging dose of insulin
332 glargine is able to improve glucose control in first few days after the first dose of IDeg.

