505 CGM, per study protocol, while remaining on their original insulin regimen, and to again
506 upload CGM data on day 5. Research staff will review this data on day 5.
507 If there is \geq 38 hours of usable CGM data from day 3-5, they will be instructed to proceed
508 with their first dose of IDeg that night, as scheduled. Subjects with $<$ 38 hours of usable
509 CGM data will be discontinued from the study.
510

511 3.10.5 Telephone Encounter #3:

512 This will be on day 4, i.e. the day after the first bedtime dose of IDeg (or on day 6 for
513 subjects who needed to repeat baseline CGM data collection). We will inquire about
514 adverse events and any change to concomitant medications. The doses of insulin
515 administered will be obtained and documented. The main purpose of this call is to ensure
516 that the subject implemented the transition from insulin glargine to IDeg, correctly. If it is
517 discovered that the subject forgot to transition, then they will be given repeat instructions
518 to dose on night of day 4. If it is discovered that the subject executed the transition
519 incorrectly, then they will need to undergo a 3-day "wash out period", during which they
520 will resume their original insulin glargine regimen (with alterations as deemed necessary
521 by study physician on day 4), and then they will be instructed to execute the transition
522 again on night of day 7. If a subject performs the transition erroneously a second time,
523 he/she will be discontinued from the study and replaced by a new subject as the study
524 supplies allow. Subjects will be instructed not to alter their dose of IDeg for at least the
525 first 3 doses (i.e. 48 hours after 1st dose).
526

527 3.10.6 CGM Removal and Download Visit (Visit 3):

528 Subjects will come in approximately 8 ± 2 days after their CGM insertion. At this visit,
529 their study CGM will be removed and downloaded. We will inquire about adverse events
530 and any change to concomitant medications. We will collect and review their study
531 logbook. They will also be given instructions on how to transition back to insulin
532 glargine.

533

534 **Once-daily glargine users:** Approximately 24 hours after their last dose of IDeg,
535 subjects will be instructed to administer 50% of their original total daily dose of glargine
536 at bedtime. At 48 hours after their last dose of IDeg, they will return to their original
537 bedtime insulin glargine dose.

538

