539 **Twice-daily glargine users:** Approximately 24 hours after their last dose of IDeg, they
540 will administer 50% of their original bedtime insulin glargine dose. Approximately 36
541 hours after their last dose of IDeg they will again administer 50% of their original
542 morning insulin glargine dose. Approximately 48 hours after their last dose of IDeg, they
543 will resume their original insulin glargine dosing regimen (i.e. 50% of total dose twice
544 daily).

545

546 Subjects will receive a gift card for \$50 for participation in the study.

547

548 3.10.7 Exit Visit/Telephone encounter #4 (Visit 4):

549 This visit will be approximately 7 days after the study CGM removal (+/- 2 days).
550 Subjects will be called to see if they have any concerns or questions. They will be
551 instructed to follow up with their original endocrinologist for any further insulin
552 adjustments.

553

554 3.11 Assessments for Efficacy

555 On the screening visit (visit 1), if there is no available record of eGFR within the last year
556 and/or hemoglobin A1c within the last 3 months, these will be obtained by venipuncture
557 at this visit. The research team nurse or physician will perform this. 2 tubes of blood (1x
558 3cc lavender and 1x 4 cc lime green) will be drawn and sent off to measure hemoglobin
559 A1c (by HPLC method) and basic metabolic panel to the UWMC clinical laboratory. No
560 extra blood will be collected from the subjects. There will be no other instances of blood
561 collection during the study. These will help ensure that appropriate subjects are enrolled
562 in the study.

563 At the various telephone encounters, study staff will verify that the subjects are following
564 study instructions correctly. Specifically, on Telephone Encounter #2, only if adequate
565 usable CGM data is available on the data uploaded by the patient will they be allowed to
566 proceed with the transition (see section 3.11.4).

567 By measuring the time a patient spends in range (TIR = 70-180 mg/dL), we are assessing
568 the efficacy of the use of IDeg as a basal insulin.

569

570

571 3.12 Assessments for Safety

572 The primary safety concern in this study is the risk of hypoglycemia. Hypoglycemia
573 management will be revised at screening visit to ensure appropriate education and all
574 medications and supplies needed to manage hypoglycemia will be prescribed at screening.
575 Subjects will be instructed that if they see BG <70 mg/dL on their personal CGM that

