576 persists longer than 15 minutes or notice symptoms of hypoglycemia regardless of
577 glucose reading, they need to perform a capillary blood glucose (CBG) measurement to
578 confirm if the meter shows a reading <70 mg/dL. If it does, they need to complete a
579 hypoglycemia episode form (Appendix B). Upon onset of a hypoglycemic episode,
580 subject is recommended to check CBG every 15 minutes until the value is \geq 70 mg/dL
581 and/or symptoms have resolved. Repeated CBG measurements and/or symptoms,
582 occurring within a period of 60 minutes after onset on a hypoglycemic episode, will by
583 default be considered as one hypoglycemic episode until a succeeding CBG value is \geq 70
584 mg/dL and/or symptoms have been resolved and should be reported as one hypoglycemic
585 episode. CBG measurements < 70 mg/dL or hypoglycemic symptoms after the 60
586 minutes period shall trigger the reporting of a new hypoglycemia episode and prompt the
587 subject to fill out a new hypoglycemic episode form until a succeeding measurement is \geq
588 70 mg/dL and/or symptoms have been resolved. In case of several low CBG values
589 within the 60 minutes interval, the lowest value is the one that will be reported as the
590 CBG value for the hypoglycemic episode but the start time of the episode will remain as
591 the time for the first CBG value and/or symptom. Whenever a subject completes a
592 hypoglycemia episode form, they should notify study staff within 24 hours. When they
593 notify study staff, details of the events around the low blood glucose (activity, food intake,
594 insulin administration) will be collected from them and then recommendations will be
595 made, as deemed necessary, by the study physician.

596 Hyperglycemia is the other risk of this study. Subjects will be instructed at screening to
597 notify study staff within 24 hours of a blood glucose >250. Study staff will try to
598 ascertain from the subject if any investigations are needed and make management
599 recommendations, as deemed necessary, by the study physician.

600 By measuring the time a patient spends above or below range (>180 mg/dL or <70 mg/dL) and assessing the frequency of use of correctional doses of short-acting insulin, we
601 are assessing how safe their glycemic management regimen is.
603

604 3.13 Patient Compliance

605 Patient compliance to study procedures will be assessed during the telephone encounters. 606

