1016 will be stored together with the remaining trial documentation.

1017

1018 **PK and/or PD Modelling**

1019 PK and PD modelling is not planned for this study.

1020

1021

1022 13. PREMATURE TERMINATION OF STUDY:

1023 All patients participating in the study will have already been taking insulin glargine prior
1024 to their enrolment in the study. Therefore, we do not anticipate patients developing any
1025 unforeseen adverse effect associated with the administration of insulin glargine. Similarly,
1026 we do not anticipate patients developing any unforeseen adverse effect associated with the
1027 administration of the placebo (normal saline).

1028

1029 IDeg will be discontinued if a patient:

- 1030 • Experiences an SAE related to IDeg (with the exception of hypo- or
1031 hyperglycemia) or an intolerable AE, such as a persistent allergy or rash.
- 1032 • Becomes pregnant or breastfeeding
- 1033 • Withdraws consent for participation in the study

1034

1035

1036

1037

1038

1039

1040

1041

1042

1043 Date and reason for drug discontinuation will be recorded on the relevant Case Report
1044 Form. Refer to Section 3.7 for Withdrawal Criteria. All study discontinuations decided by
1045 the clinician investigators will be reviewed by University of Washington's IRB. Patients
1046 discontinued from the study will be placed back on their original home insulin regimen and
1047 asked to follow up with their outpatient endocrinologists within 2-12 weeks, or at an
1048 interval deemed appropriate by their outpatient endocrinologists. Major attempts will be
1049 made to schedule an end-of-study follow-up phone call for all patients who are lost to
1050 follow-up during the course of the study.

1051

1052

1053

1054

1055

1056

1057 Patients who discontinue study drug or withdraw consent from the study prior to
1058 completion of data collection will not be replaced.

1047 14. PUBLICATION PLAN:

1048 Data and results generated from the study will be published or publicly presented at
1049 national and/or regional meetings in the form of abstracts, posters, and/or oral
1050 presentations. Clinician investigators will make good faith effort to publish data and results
1051 of this study in a peer reviewed scientific journal. The clinician investigators intend to
1052 register the study with clinicaltrials.gov.

1053

1054

1055

1056

1057 15. REFERENCES:

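### Sections 3.2, 3.10.2.1 and 3.10.5 freeze basal doses with no safety exception; nothing says whether a 3.12 physician recommendation may override the freeze, or how that patient is then analyzed

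*Combined protocol and SAP*

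**What the plan says.** **Dose freeze.** Section 3.2 states that in the 48 hours before and after the first IDeg dose "no adjustments will be made to the calculated and recommended doses of insulin" glargine or IDeg. Section 3.10.2.1 has patients take an unchanged nightly IDeg dose for the whole course of 5 ± 2 doses. In 3.10.5, "Subjects will be instructed not to alter their dose of IDeg for at least the" first three doses. None of the three contains a safety exception.

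**Clinical discretion.** Section 3.12 says "The primary safety concern in this study is the risk of hypoglycemia" and names hyperglycemia as the other risk. After a hypoglycemia episode, recommendations are to be "made, as deemed necessary, by the study physician", and similar wording covers a glucose above 250. Section 6 says patients are to receive the amount of insulin that clinicians judge appropriate, including during the study. Section 8.1 lets the clinician and the protocol together determine IDeg dosage.

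**Stopping.** Section 13 lists the cases in which IDeg will be stopped. One is that a patient "Experiences an SAE related to IDeg (with the exception of hypo- or" hyperglycemia, so glycemic events lie outside this trigger. The section also carries the pointer "Form. Refer to Section 3.7 for Withdrawal Criteria". Section 3.7 allows, but does not require, discontinuation when the investigator judges that "continuation in the trial would negatively impact the health of the patient".

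**Analysis.** Section 3.13 makes a patient non-compliant if any basal dose is missed in the 48 hours before or after the first IDeg dose. Section 12 leaves non-compliant patients out of all analyses, yet 3.8 and section 12 itself also say that every randomized participant's data will be included.

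**The concern.** The events that the protocol most expects to manage can fall in the period when it also declares the basal dose fixed. If a patient has a serious glycemic event on the first night, staff cannot tell from the text whether a recommendation under 3.12 may reach the next IDeg dose. Read literally, the freeze leaves no dose change short of withdrawal.

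Two statistical consequences follow. If staff change doses case by case, the changes will be more frequent in whichever arm has more lows or highs, and will alter that arm's post-dose time in range (TIR). And if a dose is withheld on medical advice, the patient may be classed as non-compliant and dropped. That exclusion would come after randomization and would depend on glucose, which is what the primary endpoint measures.

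**Working it through.** **1. The freeze passages compared**

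| Section | Drugs | Duration | Addressed to | Safety exception |
|---|---|---|---|---|
| 3.2 | glargine and IDeg | 48 h before and after the first IDeg dose | no one in particular | none |
| 3.10.2.1 | IDeg | all 5 ± 2 doses | patients' dosing schedule | none |
| 3.10.5 | IDeg | at least the first 3 doses | patients | none |

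The lengths differ. The impersonal wording of 3.2 can be read as binding staff too. Elsewhere the protocol does write in physician discretion: the 3.10.5 wash-out lets the study physician alter the resumed glargine regimen. No such clause accompanies the IDeg freeze.

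**2. Which IDeg dose matters for the primary endpoint**

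IDeg is taken at 2100 each night, so the first three doses fall at hours 0, 24 and 48. The post-dose TIR window runs from hour 0 to hour 48.
- Hour 0 precedes any post-dose event.
- Hour 48 falls as the window closes.
- Hour 24 is the only IDeg dose that can both respond to a post-dose event and affect 48-hour TIR.

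The event must also be known before hour 24. Section 3.12 allows 24 hours for notification, but the day 4 call in 3.10.5 asks about adverse events, so some would be known. Glargine doses before hour 0 are frozen too, but a change there precedes the blinded syringe and cannot be caused by the assigned treatment.

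**3. Why intervention could differ by arm**

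For a once-daily patient, 3.10.2.1 gives first-night basal units, relative to the usual glargine dose, of 80% + 50% = 130% with bridging and 80% with direct conversion. This is arithmetic, not a view on dosing. Section 3.9 also retains patients with known severe hypoglycemia or hypoglycemia unawareness.

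**4. Path to exclusion**

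Dose withheld on advice → basal dose not taken in the window → can be read as missed (3.13) → non-compliant → out of all analyses (section 12). A dose that is reduced but taken is not missed on the wording of 3.13. It could raise only the grounds in 3.7 for poor compliance or major protocol violation, which are not defined further.

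**5. Size, with assumed exclusions (the documents give no event rate)**

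The plan's figure first: difference 15, SD 15, 20 per arm, two-sided 0.05. Noncentrality = 15 / (15 × √(2/20)) = 3.16 on 38 degrees of freedom, giving power of 86.9% (normal approximation 88.5%). The stated 87% is reproduced.

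Power after equal losses in both arms: 85.1% with 19 per arm, 83.0% with 18, 80.7% with 17, 78.1% with 16.

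Shift in one arm's mean: if k of 20 patients are dropped and their mean change differs from the arm mean by D, the mean of those left moves by k × D / (20 − k). With D = 15 points (one planned SD, assumed):

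| k dropped | Shift (points) | Share of planned 15 |
|---|---|---|
| 1 | 15/19 = 0.8 | 5% |
| 2 | 30/18 = 1.7 | 11% |
| 3 | 45/17 = 2.6 | 18% |
| 4 | 60/16 = 3.75 | 25% |

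The direction depends on which arm loses patients and whether their TIR was better or worse than average. The documents settle neither.

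**The case against.** A reader might infer that a site is given opposite instructions, or that section 13 obliges a patient to stay on IDeg after a serious hypoglycemic event. The documents do not support either reading. Section 13 removes an automatic stop and does not forbid stopping. It sends the reader to 3.7, which has no glycemic exception. A mandatory list beside a discretionary one is ordinary structure. Section 3.12 does not direct a basal change: its recommendations may concern food, activity or bolus insulin, and correction insulin above 250 is already allowed in the window. Section 3.10.5 instructs patients and is not worded as a limit on the physician. Sections 6, 10.6 and 10.8 provide for prompt treatment, medical care, glucagon and access to providers. The trial is single-center, so differing practice between sites cannot arise.

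A reader might also take the share of planned IDeg doses under a freeze as the size of the problem. That counts doses, not events or bias, and the step-by-step timing leaves essentially one dose that bears on the primary endpoint. Nor does any passage class physician-directed care as a protocol violation; that is only a possible reading of undefined terms.

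All of this stands. It does not answer the narrower question. Nothing says whether a 3.12 recommendation may change or withhold a frozen dose. Section 13 requires date and reason for drug discontinuation, but not for a single dose changed or withheld. The route from a withheld dose to exclusion remains open.

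**Conclusion.** The point holds as an unreconciled ambiguity with an analysis consequence. Three freezes of different length, without a safety exception, stand beside open physician discretion in 3.12, 6 and 8.1, and no passage is said to prevail. A dose withheld on medical advice can be read as non-compliance and lead to an exclusion related to the outcome, while 3.8 and part of section 12 promise that everyone is included.

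The size is unknown because no event rate is given. On the assumed one to four exclusions in an arm of 20, each differing from the arm mean by 15 points, that mean moves by 0.8 to 3.75 points, against a planned difference of 15. With no such event the effect is nil. This is a clarification worth making because it is cheap. It does not invalidate the design, and it implies no view on which clinical rule is right.

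**What to change.** Reconcile 3.2, 3.10.2.1, 3.10.5, 3.12, 6, 8.1, 3.7 and 13 so that one named passage governs a serious glycemic event during the freeze and the others refer to it. Give the freeze one stated duration. The clinical content is for the investigators.

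For the analysis, state in 3.7, 3.13 and 12 that a basal dose changed or withheld on the study physician's advice:
- is recorded with date and reason;
- is neither a protocol violation nor non-compliance;
- does not remove the patient's CGM data from the primary comparison.

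Resolve the two conflicting inclusion statements in section 12 in the same amendment.

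Cost: amendment wording in these sections and one CRF field. The downside is that a few patients' post-dose TIR may include a safety-driven change; the recorded date and reason allow these patients to be identified and reported.
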